## 7.2. Compliance

Study medication should be used in accordance to the study protocol. The Principal Investigator, or a member of the team, will be responsible for administering the study medication. The researcher team will record used and unused medication for each trial patient on a Medication Record Sheet. This Record Sheet will be available for monitoring visits in accordance with RD 223/2004. To ensure traceability of the study, for NaCl intravenous, the following will be noted: trade name, quantity and lot number dispensed at each visit. This information will also appear in the EDC. In the case of common salt (capsules), a record will be kept of those given to the patient and of the blisters returned by the patient at the 24h visit after the contrast. In this way, the patient's adherence to the treatment will be assessed.

## 8. EFFICACY ASSESSMENT

### 8.1. Efficacy assessment criteria

- Increase in serum creatinine from baseline greater than 0.3 mg/dL.
- Reduction of the estimated glomerular filtration rate greater than 25% from baseline value.

## 8.2. Development of the study

Patients will undergo the following procedures:

Screening visit (from two months to 48 hours before the procedure): verification of inclusion and exclusion criteria. Signature of the informed consent. A laboratory blood test will be recorded within two months from the CE-CT scan. The screening visit may take place on the same day as randomization (visit 1).

Visit 1 (from two months to 48 hours before the procedure): review of inclusion and exclusion criteria. Serum creatinine, eGFR and ions will be checked. Registration of demographic and clinical data. The patient will be randomized and will receive therapeutic information to the assigned group. In the case of the oral sodium chloride arm, capsules will be provided.

Visit 2 (day of the procedure): Before the contrast administration, the investigator will ensure the patient has taken study medication. A physical examination will be performed. Furthermore, blood and urine samples will be collected for the specific analytical determinations and biomarkers. After that, contrast will be administered as well as the intravenous sodium chloride (intravenous arm). Adverse events will be reported.

Visit 3 (24 hours after contrast): The investigator will perform a physical examination, will ensure the compliance of study medication (oral NaCl arm), and will report the adverse events. Moreover, blood and urine samples will be collected.

Visit 4 (48 hours after contrast): same evaluation as visit 3, excluding compliance assessment.

### Study Flowchart

	SCREENING (From two months to 48 hours before the procedure)	VISIT 1† (From two months to 48 hours before the procedure)	VISIT 2 (Day of the procedure; 0 hours)	VISIT 3 (24 hours after contrast)	VISIT 4 (48 hours after contrast)
Inclusion and exclusion criteria	X	X			
Informed consent	X				
Randomization		X			
Medical history		X			
Clinical variables		X	X	X	X
Contrast administration			X		
Study treatment administration		X*	X		
Evaluation of treatment compliance			X	X*	
Clinical laboratory assessments	X		X	X	X
Biomarkers			X	X	X
Adverse events evaluation		X	X	X	X

\* Patients in oral NaCl arm.

† The screening visit may take place on the same day as randomization (visit 1).

### **8.3. Methods for efficacy assessment**

The determinations of the study will be performed prior to contrast administration, and at 24 and 48 hours after the CE-CT scan.

- Plasma creatinine, ions, cystatin C, blood count and venous gasometry will be assessed.
- NGAL\*, KIM-1\*, NAG\*, t-gelsolin\*, GM2AP\*, and urinary creatinine will be determined to homogenize the values of the different biomarkers. Sodium, pH, microalbuminuria and proteinuria will also be measured in urine.
- 

These analyses will be performed in the laboratories of the Hospital Universitario Ramón y Cajal, as part of the clinical routine, except for the biomarkers identified with an asterisk. These samples will be stored at -80°C in the Laboratory of the Heart Failure and Vascular Risk Unit of the Internal Medicine Dept. Working conditions guarantee traceability, quality and safety storage control and processing.

The methods for the different determinations are presented below:

- Creatinine in blood and urine: using the alkaline picrate colorimetric technique (kinetic Jaffé) on the Architect 16000 analyzer (Abbott Diagnostics).
- Cystatin C in blood: by turbidimetric technique on the Architect 16000 analyzer (Abbott Diagnostics).
- NAG: by commercial kit (Roche Diagnostics) based on spectrophotometric detection of the reaction product catalyzed by NAG.
- NGAL: by chemiluminescence detection techniques on the Architect 2000 immunoassay analyzer (Abbott Diagnostics).
- T- Gelsolin: by Western blot.
- KIM 1: by commercial ELISA kit (CUSABIO).
- Ganglioside M2 activating protein (GM2AP): by Western blot.

## **9. SAFETY**

Safety assessments will be carried out in accordance with the Standards of Good Clinical Practice (GCP) and current legislation.

### **9.1. Definitions**

#### **Adverse Event (AE)**

Any untoward health occurrence in a patient or clinical trial subject treated with a drug, even if not necessarily causally related to that treatment. An AE can be any unfavorable and unintended sign, symptom, or disease temporally associated with the use of an investigational product, whether or not related to the investigational product.

#### **Adverse Reaction (AR)**

An unintended, harmful reaction to an investigational product, regardless of the dose administered. In this case there is a suspected causal relationship between the investigational product and the AR.

#### **Serious Adverse Event (SAE) and Serious Adverse Reaction (SAR)**

Any adverse event or adverse reaction that, at any dose, results in death, threatens the life of the subject, requires hospitalization of the patient, or prolongs an existing hospitalization, causes permanent or significant disability or incapacity, results in a congenital anomaly or malformation.

Suspected AA or AR that are considered medically significant, even if they do not meet the above criteria, will also be treated as serious, including major medical events that require intervention to prevent the occurrence of one of the consequences described above. Likewise, all suspected transmission of an infectious agent should be reported as serious.

#### **Unexpected Adverse Reaction (UAR)**

Any AR whose nature, intensity or consequences do not correspond to the reference information for the medicinal product.

#### **Minimum information to be specified**

The researcher team will follow up on the possible adverse events that could arise throughout the study. Thus, analytical safety parameters will be determined periodically and the patient will be asked at each visit if he/she has experienced any type of symptomatology since the previous visit. If it exists, it will be reflected in the clinical history and in the data collection sheet. The information regarding the time of appearance, duration, intensity, course and outcome will be recorded. In addition, all patients in the study will be given a diary to record anything they consider of interest, including possible AEs. The reporting of serious or unexpected adverse events will be done according to Spanish legislation. All adverse events should be documented in the patient's medical record.

### **9.2. Causality assessment**

Researches will take into account all aspects related to adverse reactions, contraindications, warnings and precautions for use, and possibilities of interactions with other drugs, as specified in the data sheets of the investigational drugs. Safety parameters to be measured are described in the section 6.2.

### **9.3. Safety assessment**

Adverse events in this study will be classified on the basis of their causal relationship with the drug as:

- **Possibly/probably related:** if there is reasonable suspicion of a possible or probable relationship (reasonable temporal sequence between the administration of the investigational product and the occurrence of the adverse event and the AE cannot reasonably be attributed to any alternative cause).
- **Unrelated:** there is a reasonable time sequence between the administration of the investigational product and the occurrence of the adverse event, but the adverse event can be explained by alternative causes; or there is no reasonable time sequence between the administration of the drug and the occurrence of the adverse event.

The investigator should evaluate the causality of all serious adverse events. In the event that the investigator does not know causality, for reporting purposes the adverse event should be considered to be related to the investigational product.

### **9.4. Intensity assessment**

For all AR observed the investigator will use the following definitions to rate the intensity of any AR collected during the study in the EDC:

- Mild: that which does not cause limitation in daily activities.
- Moderate: that which causes some limitation in the performance of daily activities.
- Severe: that which prevents the performance of daily activities.

## **9.5. Severity assessment**

AR should also be classified on the basis of their severity. In general, if they meet any of the following criteria should be considered serious adverse reactions:

- Life-threatening.
- Requiring hospitalization or prolongation of an existing hospitalization.
- Causing permanent or significant disability or incapacity.
- Result in congenital anomaly or malformation.
- Considered medically important, understood as that which requires urgent intensive treatment to avoid one of the outcomes.

## **9.6. Expectancy assessment**

An AE not listed in the drug label.

## **9.7. Safety recording procedure**

Researcher team should record all AR specifying the date of initiation, intensity, severity, action taken and outcome. If any treatment is given for the AR, it should be recorded in the EDC. All ARs should be recorded in each subject's EDC.

## **9.8. Safety reporting procedure**

The investigator will immediately report all AR to the sponsor (always within 24 hours of knowledge) on the form designed for this purpose (Reporting Form). This form, after being completed and signed by a member of the researcher team, will be sent in paper format by fax to the Clinical Trials Unit of the Hospital Universitario Ramón y Cajal ([contact], Unidad de Ensayos Clínicos, Hospital Universitario Ramón y Cajal, [name]). The initial communication will be followed by detailed written communication. The investigator must follow up all the AR until resolution, return to baseline or stabilization in case of permanent involvement. Initial and follow-up communications should identify trial subjects by a specific code number. The sponsor will keep a detailed record of all AR reported by the researchers. These records should be submitted to the AEMPS and the IRB/IEC upon request. The notification period will be from the moment the patient signs the informed consent until 30 days after the administration of the last dose. After this period, only those serious AR related to the study medication of which the investigator is aware should be reported to the sponsor.

### **Report of suspected serious AR and unexpected AR**

The sponsor will notify all the suspected serious and unexpected adverse reactions associated with the product to the AEMPS (Agencia Española de Medicamentos y Productos Sanitarios) Clinical Trials Area of the Department of Medicines for Human Use; the Ethics Committee involved and the Autonomous Communities delegates where the clinical trial is performed. Notification period will be 15 days, except when the suspected AR has caused the death of the subject, or endangered his life, which will be communicated within 7 days after its knowledge.

## **9.9. Follow-up plan**

When an AR occurs, it will be recorded as specified in this protocol and the patient will be followed-up until it is considered resolved.

## **9.10. Notification of other safety information**

The sponsor should also report any information that could change the benefit of the research product or that could lead to changes in the schedule of administration of the trial, such as:

- A qualitative change or an increase in the percentage of occurrence of unexpected and severe AR.
- Unexpected and severe AR occurring after completion of the trial and reported by the investigator to the sponsor.
- New events related to the conduct of the trial or the development of the research product and likely to affect patient safety such as: AR that may be associated with the trial procedures and may modify the conduct of the trial, lack of efficacy in a drug used for the treatment of a life-threatening disease, new safety findings from new animal studies (such as carcinogenicity), any premature termination or temporary halt of a clinical trial with the same research product for safety reasons, conducted in another country by the same sponsor, any recommendation from the Data Monitoring Committee that is relevant to patient safety. This information will be notified as soon as possible and no later than 15 days after the sponsor has become aware of it. Additional information will also be notified as soon as possible.

## **9.11. Annual safety reports**

The annual safety reports, which will include the RAGIs collected in the study, will be sent by the sponsor to the AEMPS (Clinical Trials Area of the Sub-Directorate General for Medicinal Products for Human Use), the Autonomous Regions and the CEICs involved, within the deadlines established in the legislation in force.

## **9.12. Notification to investigators**

The sponsor should notify the researcher of any information that could affect the safety of the trial subjects as soon as possible. The information on unexpected and severe AR will be sent annually in a list together with a brief analysis of the data provided. Researchers will also be informed of any safety issues impacting the conduct of the clinical trial or product development, including discontinuation of the development program or safety-related protocol modifications.

## **9.13. Access to the randomization code during the trial**

In case of adverse events, the treatment assignment number from the randomization code list will be disclosed under special circumstances. If possible, the delegate should be contacted before the number is disclosed. Each patient will have a randomization code which contains the treatment assignment. It should be kept in a safe place throughout the clinical trial. The researcher is responsible for the integrity of the

randomization list. If a treatment assignment is unblinded, the researcher will record the date and reason in the EDC. Unblinding should not be a reason for withdrawal the product or the patient from the study.

## 10. STATISTICAL CONSIDERATIONS

### 10.1. Sample size calculation

The sample size of the trial was calculated to be able to show the non-inferiority of oral sodium chloride to intravenous prophylaxis with regard to the primary study endpoint in outpatients undergoing a contrast-enhanced CT scan. The calculation was based on an expected PC-AKI incidence of 7% in the intravenous arm and 12% in the oral arm. Accordingly, considering a non-inferiority margin of 5%, a power of 80% and a one-sided p-value of 0.025, the required sample size is 266 patients, 133 per arm.

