### **5.3. Study design**

PNIC-Na is a phase 2, monocenter, randomized, open-label, non-inferiority trial. Two types of preventive treatment will be compared in patients undergoing a CE-CT scan:

- Oral prophylaxis with NaCl capsules and free water intake (250 mL of water with each capsule, ensuring a water intake of 750 mL/day) in the 48 hours prior to contrast exposure (n=133). It will be performed on an outpatient basis at a dose of 100 mg/kg body weight distributed in 60 hours, 48 hours prior to the procedure and 12 hours after. Appendix C describes the specific dose according to weight.
- Intravenous prophylaxis with 0.9% NaCl before and after contrast exposure (n=133). It will consist of in-hospital administration of 3 mL/kg in the hour before and 2 mL/kg in the 4 hours after the procedure.

The contrast used will be iodixanol (320 mg iodine/mL, infusion rate 2-5 mL/sec).

The corresponding treatment will be administered after medical prescription, validation by the pharmacist and confirmation. The nurse in charge of the patient will administer the treatment. The intravenous prophylaxis schedule for the study will begin in the Radiology Department of the Hospital, and will conclude in the Clinical Trials Unit of the same center.

The study will consist on the schedule of visits described in section 9.2.

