## **6.3. Sample size and justification**

The study will be conducted in 266 individuals on an outpatient basis. Taking into account the non-inferiority design, for the determination of the sample size it has been considered acceptable to establish a priori a difference of no more than 5% in the incidence of PC-AKI of oral prophylaxis with respect to intravenous. Considering our high-risk population, we estimated an incidence of PC-AKI in the intravenous group of 7% and 12% in the oral group. With this expected response, a non-inferiority margin of 5%, a power of 80% and a degree of significance of 2.5%, the sample size will be 266 patients, 133 per group.

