### 10.3. Statistical methods

A description of the study sample stratified by randomly assigned treatment will be made. Categorical variables will be described by absolute and relative frequencies. Quantitative variables will be described by the mean and standard deviation (or median and interquartile range in the case of highly asymmetric distributions). For the analysis of the primary endpoint of the study, the univariate comparison of the proportions of PC-AKI events within 48 hours after intravenous contrast administration in both arms will be carried out. The 95% confidence interval of the difference in proportions will be calculated and displayed graphically. All analyses will be intention-to-treat and per-protocol. For the main objective a p-value less than 0.025 (unilateral) will be considered as statistically significant. All other group comparisons will be of an exploratory nature. Subgroup analyses will be performed for the risk factors defined as inclusion criteria. For exploratory contrasts, a p-value less than 0.05 (two-sided) will be considered as statistically significant.

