#### **14.5. Amendments to the protocol**

Neither the investigator nor the monitor or the sponsor will modify this protocol without first obtaining the consent of the other parties. The modification should be documented in writing. Any changes in the research activity, except those necessary to eliminate an immediate apparent risk to the patient, should be reviewed and approved by the IRB/IEC prior to implementation. Amendments to the protocol should be submitted by the sponsor to the health authorities, and modifications may require review and approval by the IRB/IEC.

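### The assumed PC-AKI rates (IV 7%, oral 12%) differ by exactly the 5-point margin, so 133 per arm gives about 2.5% power, not 80%

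*Combined protocol and SAP*

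**What the plan says.** Section 5.3 describes the design: "PNIC-Na is a phase 2, monocenter, randomized, open-label, non-inferiority trial". Section 6.3 sets the acceptable limit as "a difference of no more than 5% in the incidence of PC-AKI of oral prophylaxis with respect to intravenous", so the margin is an absolute difference in incidence, oral relative to intravenous. The same section gives the planning rates: "we estimated an incidence of PC-AKI in the intravenous group of 7% and 12% in the oral group". Section 10.1 repeats them, "The calculation was based on an expected PC-AKI incidence of 7% in the intravenous arm and 12% in the oral arm", and adds the remaining inputs: "considering a non-inferiority margin of 5%, a power of 80% and a one-sided p-value of 0.025". Both sections conclude that 266 patients, 133 per arm, are required.

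The planned analysis is on the same scale. Section 10.3 compares the two proportions at one-sided 0.025 and adds: "The 95% confidence interval of the difference in proportions will be calculated and displayed graphically". Section 10.6 makes the per-protocol analysis the main one. Neither sample size section mentions an allowance for exclusions or losses.

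**The concern.** PC-AKI is an adverse outcome, so a higher rate in the oral arm counts against oral. A non-inferiority trial has power to the extent that the true difference lies inside the margin. Here the assumed difference is on the margin, which is the boundary of the null hypothesis. A calculation that returns a finite sample size with 80% power from these inputs cannot be right.

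This calculation is the only justification given for 266 patients. If the stated rates are true, the trial would almost certainly fail to show non-inferiority. A reader who trusts the 80% would then take a missed margin as good evidence against oral prophylaxis, when most such results would be inconclusive.

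**Working it through.** **Inputs.** From Sections 6.3 and 10.1: pIV = 0.07, pOral = 0.12, margin 0.05, one-sided alpha 0.025, power 80%, 133 per arm. Allocation is 1:1 (Section 5.4).

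**Formula** (standard, unpooled variance, harmful event):

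n per arm = (1.960 + 0.842)² × [pIV(1 - pIV) + pOral(1 - pOral)] / [0.05 - (pOral - pIV)]², where the squared term in front is 7.849.

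Power = Φ{[0.05 - (pOral - pIV)] / SE - 1.960}, with SE = √{[pIV(1 - pIV) + pOral(1 - pOral)] / n}.

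**1. Reproducing 133.** The variance term is 0.07 × 0.93 + 0.12 × 0.88 = 0.0651 + 0.1056 = 0.1707. If the 5 points favour oral (IV 12%, oral 7%), the distance to the margin is 0.05 + 0.05 = 0.10, and n = 7.849 × 0.1707 / 0.10² = 133.98. Power is 79.7% at 133 and 80.0% at 134. The stated figure is this value rounded down.

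**2. The inputs as written.** The distance is 0.05 - (0.12 - 0.07) = 0. The denominator is zero, so no finite n exists, and power = Φ(-1.960) = 2.5% at any n.

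**3. Other readings, per arm.** None gives 133.
- Equal rates of 7%: 7.849 × 0.1302 / 0.05² = 408.8, so 409.
- Equal rates of 12%: 663.1, so 664.
- Equal rates at one-sided 0.05: 322 at 7%, 523 at 12%.
- Superiority test of 7% against 12%, two-sided 0.05: 539.
- A 10-point margin with a true difference of 5 points: 536.

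**4. Power at 133 per arm, 5-point margin.** The exact columns enumerate two Binomial(133, p) counts and declare non-inferiority when the upper 95% limit is below 5 points. The equal-rate rows are illustrations, not assumptions from the documents.

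| True rates (IV / oral) | Formula | Exact, Wald | Exact, Newcombe |
|---|---|---|---|
| 7% / 12% (as stated) | 2.5% | 2.9% | 2.5% |
| 12% / 7% | 79.7% | 81% | 79% |
| 7% / 7% | 36% | 37% | 33% |
| 12% / 12% | 24% | 25% | 24% |

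**5. What the trial would report at the stated rates.** The 95% interval would include both 0 and 5 points in about 68% of trials (Newcombe 70%). Its lower limit would be above 0 in about 29% (Newcombe 28%).

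**6. In event counts.** Suppose 9 of 133 IV patients have an event (7% of 133 is 9.3). Wald intervals for oral minus IV, in points, are:
- 7 oral events: -7.2 to 4.2 (margin met)
- 8 oral events: -6.6 to 5.1 (inconclusive)
- 18 oral events: -0.4 to 14.0 (inconclusive)
- 19 oral events: 0.2 to 14.8 (oral worse)

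Newcombe intervals give the same cut-offs. With 9 IV events, the oral arm must show fewer events than the IV arm to meet the margin.

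**The case against.** The most charitable reading is that 12% is not an expectation but the tolerated ceiling, 7% plus 5 points, with the arms assumed equal at 7%. The wording is against this: both sections present 12% as the expected or estimated oral rate. The arithmetic is too, since equal 7% rates need 409 per arm.

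A second reading is that the rates were swapped in writing. That would reproduce 133, but IV 7% and oral 12% stand in the same order in both sections, so a single slip is unlikely. It would also make the 80% depend on oral being truly 5 points better, which the protocol never claims. Because no formula or software is named, the reversed direction remains an inference about the source.

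Three objections to the remedy have weight:

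- The restated power assumes 133 evaluable patients per arm, while the main analysis is per protocol. If, as an assumption, 5%, 10% or 15% were excluded (126, 120 or 113 per arm), the formula power at IV 12%, oral 7% falls to 77.5%, 75.5% or 73.0%, and at equal 7% rates to 34%, 33% or 31%. The 2.5% at the stated rates does not change.
- Section 10.3 already plans the confidence interval, so a sentence on how to read a missed margin is a useful addition rather than the correction of an error.
- The sponsor need not print many scenarios; the intended rates and the matching power are what matter.

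**Conclusion.** The sample size statement is wrong as written and must be corrected. With IV 7%, oral 12%, a 5-point margin and one-sided 0.025, power is about 2.5% at 133 per arm, and 80% is unattainable at any size. This needs only the documents' own figures and the fact that PC-AKI is a harm; the normal approximation and exact enumeration agree. The 80% holds only if oral is assumed truly better, for example IV 12% and oral 7%. If the arms were equal at either planned rate, 133 per arm would miss the margin more often than meet it. Apart from the 2.5%, these power figures assume no per-protocol exclusions and would be lower with them.

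**What to change.** In Sections 6.3 and 10.1:

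- Remove the claim that 266 patients give 80% power at IV 7% and oral 12%.
- State the true rates actually intended. If they were IV 12% and oral 7%, say so, and say that the power (79.7% at 133 per arm) depends on oral being truly better.
- Restate the power of 133 evaluable patients per arm: 2.5% at IV 7%, oral 12%, and about 80% at IV 12%, oral 7%. At least one equal-rate figure, labelled as an illustration, would help the reader: about 36% with both arms at 7%, where 409 per arm would be needed for 80%.
- Note that the main analysis is per protocol, so exclusions reduce these figures.
- State that 266 is kept with the restated power, or give the re-derived number.

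Optionally, add to Section 10.3 that a 95% interval containing both 0 and 5 points is inconclusive and that a lower limit above 0 is evidence that oral is worse, and say which analysis set governs.

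The cost is an amendment with ethics review. Section 14.5 states: "Amendments to the protocol should be submitted by the sponsor to the health authorities". Section 10.5 also requires approval, by amendment, of deviations from the statistical plan. The stated power becomes less favourable, but correcting it needs no extra patients. Powering for equal 7% rates would take 2 × 409 = 818 patients, or 818 / 8 = about 102 months at the 8 per month planned in Section 5.6; this point does not ask for that.

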## **5.9. Randomization**

The Clinical Biostatistics Unit of Hospital Universitario Ramon y Cajal will generate (by computer) a randomization list to assign each treatment. The ratio will be 1:1. This list will be sent to the Pharmacy Department of the hospital, which will be responsible for supplying the study researchers with the treatment corresponding to the patient number in the trial.

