## **6.4. Withdrawal criteria and analysis**

The patient may discontinue participation in the study at any time he/she wishes. The investigator/physician may also decide to withdraw a patient from the trial if the patient does not meet the protocol standards. Patients will terminate their participation in the study for the following reasons:

- Completion of treatment according to the study protocol.
- Medical safety reasons.
- Serious adverse effect or adverse effect that the Investigator considers unacceptable.
- Voluntary withdrawal by the patient.
- Death.
- Acknowledgement during the follow-up that the patient did not meet the selection criteria for the clinical trial.

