## **10.6. Selection of subjects for analysis**

All analyses will be by intention to treat and by protocol. Since the study is a non-inferiority study, the main analysis will be per protocol.

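### The 133 per arm required for 80% power is also the planned size of each arm, yet the main analysis is per protocol and no allowance for exclusions is stated

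*Combined protocol and SAP*

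**What the plan says.** Section 6.3 states that "the sample size will be 266 patients, 133 per group", and section 10.1 repeats it as a requirement: "the required sample size is 266 patients, 133 per arm". Both tie the figure to 80% power, a 5% non-inferiority margin and "a one-sided p-value of 0.025". The incidence assumption in 10.1 is an "expected PC-AKI incidence of 7% in the intravenous arm and 12% in the oral arm".

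The same 133 is then the number of patients planned for each arm. It appears that way under Study population in the Summary, in the description of the two arms in section 5.3, and under both treatments in section 5.5. Section 5.6 gives 266 as the number of patients to be included.

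On the analysis set, section 10.3 plans both intention-to-treat and per-protocol analyses, and section 10.6 decides between them: because the trial is one of non-inferiority, "the main analysis will be per protocol". The per-protocol set is not defined. No section gives a dropout or non-evaluable allowance, a replacement rule, an expected per-protocol size, or a statement that 133 counts evaluable patients.

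Several sections describe ways in which a patient could leave such a set. Section 6.4 lists reasons for ending participation, including voluntary withdrawal, ineligibility found during follow-up, and "Serious adverse effect or adverse effect that the Investigator considers unacceptable". Section 7.2 counts returned capsules to assess adherence. Section 7.1 prohibits nephrotoxic agents around the procedure. Section 10.4 provides for uncollected primary outcomes, but only in sensitivity analyses.

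**The concern.** A power figure belongs to a particular number of analysed patients. Here the number computed as necessary equals the number to be enrolled, while the deciding analysis uses a subset of those enrolled. If anyone is excluded, the 80% no longer describes the analysis that decides non-inferiority.

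At stake is how the result is read. A wide interval or a failure to show non-inferiority would be judged against a precision that the main analysis was not planned to have. The gap would also survive a correction of the incidence assumptions: if a new sample size is calculated and again equated with the number enrolled, the same omission returns.

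**Working it through.** **Inputs.** One-sided alpha 0.025, power 80%, margin 5 points, 133 per arm (sections 6.3 and 10.1); 1:1 allocation (section 5.9). The margin is absolute, oral minus intravenous: "a difference of no more than 5% in the incidence of PC-AKI of oral prophylaxis with respect to intravenous". PC-AKI is a harm, so lower is better. The documents give no exclusion rate; 5%, 10% and 20% are assumptions, giving 133 × 0.95 ≈ 126, 133 × 0.90 ≈ 120 and 133 × 0.80 ≈ 106 per arm.

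**Formulas** (normal approximation, unpooled variance; d = oral minus intravenous incidence):

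- SE = √{[pIV(1 − pIV) + pOral(1 − pOral)]/n}
- power = Φ[(0.05 − d)/SE − 1.96]
- n per arm = [pIV(1 − pIV) + pOral(1 − pOral)] × (1.960 + 0.842)²/(0.05 − d)²

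**Step 1: the plan's own figure.** As written, d = 0.12 − 0.07 = 0.05, which equals the margin. The denominator of n is zero, so no finite sample size gives 80%. Power is Φ(−1.96) = 2.5% at every n.

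Other readings tried do not give 133 per arm: 7% in both arms needs 409; a 10-point margin with 7% and 12% needs 536; a superiority comparison of 7% with 12% needs 539.

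The figure appears only if the direction is reversed (intravenous 12%, oral 7%, so d = −0.05 and the distance to the margin is 10 points):

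n = (0.0651 + 0.1056) × 7.849/0.01 = 133.98, or 134 after rounding up. At 133 per arm, power is 79.7%.

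**Step 2: power on that reversed reading.**

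| Assumed exclusions | Analysed per arm | SE | 0.10/SE | Power |
|---|---|---|---|---|
| 0% | 133 | 0.0358 | 2.791 | 79.7% |
| 5% | 126 | 0.0368 | 2.717 | 77.5% |
| 10% | 120 | 0.0377 | 2.651 | 75.5% |
| 20% | 106 | 0.0401 | 2.492 | 70.3% |

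The losses are 2.2, 4.2 and 9.4 points. Exact binomial enumeration agrees: 80.8% with Wald and 79.2% with Newcombe intervals at 133, and 71.3% and 69.1% at 106.

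**Step 3: 7% in both arms.** Here d = 0, and the 95% CI half-width is 1.96 × √(2 × 0.07 × 0.93/n).

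| Analysed per arm | Power | Half-width (points) |
|---|---|---|
| 133 | 35.9% | 6.1 |
| 120 | 32.9% | 6.5 |
| 106 | 29.7% | 6.9 |

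**Step 4: does the shortfall hold for every pair of incidences?** No. At 106 per arm, intravenous 12% with oral 6% still gives 80.3%, and intravenous 7% with oral 2% gives 94.3%. At the stated 7% and 12%, power is 2.5% with or without exclusions.

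**The case against.** The strongest objection is one of proportion. With 7% in both arms, power is 35.9% at 133 per arm, about 44 points below the stated 80%; excluding 10% takes off a further 3 points. The incidence assumption is by far the larger problem, and an allowance for exclusions cannot cure it. That stands, and this point must come second to it.

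A reader might infer that the deciding analysis has less than 80% power whatever incidences are assumed. The documents do not support this. At the stated incidences the shortfall is not caused by exclusions, and at sufficiently favourable incidences power stays above 80% even after 20% exclusions. Per-protocol incidences may also differ from those in all randomised patients, so the effect need not act through sample size alone.

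A reader might also infer that the plan forecasts losses. It does not. Section 6.4 lists reasons why participation may end, the first being completion; sections 7.1 and 7.2 attach no analysis consequence to prohibited drugs or poor adherence; and section 10.4 forecasts no missing outcomes. Follow-up ends 48 hours after contrast, and nothing in the documents supports 20% in particular. The assumed rates only show sensitivity.

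Finally, section 10.1 does not say that 133 are randomised. That reading rests on the same number being the planned group size elsewhere, and no other natural reading is available.

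What survives is that required and enrolled numbers are equal, the main analysis set can be smaller, and the plan does not say by how much or with what power.

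**Conclusion.** The point holds in limited form. Under any assumptions for which 133 analysed per arm gives just 80%, the main per-protocol analysis has less than 80% power once patients are excluded, and the plan makes no provision for this. On the one reading that gives about 133, which reverses the direction stated in section 10.1, the loss is roughly 2 to 9 points for assumed exclusions of 5% to 20%. With 7% in both arms it is about 3 to 6 points at 10% to 20% exclusions, from a base of 35.9%.

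These sizes rest on the normal approximation, on exclusion rates that are assumed, and on incidences that are the same in the per-protocol set as in all randomised patients. The matter is worth correcting because the unqualified 80% is not tied to the analysis that decides the trial, but it ranks below the fault that the expected difference equals the margin.

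**What to change.** When the incidence assumptions in sections 6.3 and 10.1 are corrected, make these changes in the same places:

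- State that 133 per arm is the number randomised, and give the expected size of the per-protocol set.
- Replace the unqualified 80% with the power and the 95% CI half-width for the per-protocol set, under the corrected incidences, over a stated range of retention (for example 90% and 80%).
- Label the retention rates as assumptions.

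The cost is wording in the protocol and its statistical section. The stated power will look less favourable. This change by itself requires no extra enrolment; whether 266 remains adequate depends on the corrected incidences and is a separate decision.
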